2.1 Overall study design

This is a multinational, multicenter, retrospective, observational study of antidepressant drug utilisation among an inception cohort of patients under specialists (psychiatrists) care who are prescribed Seroquel XR for treatment of major depressive episodes associated with MDD following launch of the indication in each country. The study will be conducted in 5 European countries: Germany, Italy, Romania, Spain, and Sweden to ensure geographic representation across European member states. The sponsor may include alternate EU country(ies) based upon limited use of Seroquel XR for MDD in the countries listed and whose selection will maintain geographic representation among EU countries.

The inception cohort is defined as patients initiating Seroquel XR (as add-on therapy or as monotherapy) during a 9 month period corresponding to 3 to 12 months following the launch of the product in each country for the MDD indication. In the period immediately after launch, physicians may not be aware of the approval of Seroquel XR for add-on treatment for MDD. Therefore, patients treated with Seroquel XR within the 3 months after launch will not be included in the inception cohort because they are not likely to be representative of patients

[figure not shown]
treated in subsequent periods. A drug utilisation questionnaire will be used to collect study data. Data collection will be initiated following a study-defined index date, approximately 12 months after product launch. All study sites within a country will be assigned the same index date and will not be contacted prior to the index date.* Initiation of site-specific activities for selection of patient records meeting study selection criteria will commence on or following the index date. Data on drug utilisation will be censored on the index date. This approach will ensure that study procedures do not influence prescribing practices.

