4.2 Questionnaire Administration

4.2.1 Timeline for questionnaire administration

The exact index date for each country will be selected to optimise preparations leading to completion of drug utilisation questionnaires at all sites within a country following Good Pharmacoepidemiology Practices (PDS 2008).

Contact with investigators and site preparatory activities are initiated following the index date, which will correspond to a date approximately 12 months following the launch of Seroquel XR for MDD in each country.

Preparatory activities for completion of the drug utilisation questionnaires at each site will rely on automated and manual review of data from patient medical records in order to identify patients meeting study inclusion criteria. This selection includes consideration of the inception cohort definition (i.e., initiation of treatment with Seroquel XR in the time interval 3 months after launch up to the index date).

Once site preparatory activities are concluded, including the obtaining of informed consent from the patient, data abstraction of patient medical records using the drug utilisation questionnaire will begin.

Information on the Physician questionnaire related to physician characteristics will be completed based upon the best available recollection by the investigator. Patient questionnaire data will be abstracted from the medical records of the patients maintained at the official location for storage of records for the site/investigator and will be performed by a representative of AstraZeneca.

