9.2 Patient's demographic data and psychiatric history

Summary statistics will be provided by country and overall for patient's demographics data including age, gender, and race, and for patient's medical history including years since first depressive episode, year of MDD diagnosis, number of depressed episodes over lifetime, number of depressive episodes during the 12 months up to the latest consultation, presence of psychotic symptoms in the past, presence of psychotic symptoms at start of Seroquel XR

treatment, psychiatric co-morbidities (anxiety disorders, substance use, other Axis I, or other Axis II disorder), other medical co-morbidity (hypertension, obesity, diabetes, other cardiovascular disorder), ever been hospitalised for a psychiatric condition), as well as for the number of visits to the psychiatrist during the timeframe that Seroquel XR has been prescribed.

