(1) Specific drug name (generic or brand names)	(2) Start date (day/mth/year) Check for “on demand” or prn use)	(3) End Date (day/mth/year)	(4) Dose (specify Unit)	(5) Did the dose change at initiation of Seroquel XR?	(6) Most recent dose prior to [INDEX DATE] (if different than at initiation)	(7) Date of most recent dose change (day/mth/year)
	___/___/___  prn	___/___/___  Still prescribed at [INDEX DATE]	_____	 Increase  Decrease  Remained the same  Not applicable	_____  Not applicable	___/___/___  Not applicable
	___/___/___  prn	___/___/___  Still prescribed at [INDEX DATE]	_____	 Increase  Decrease  Remained the same  Not applicable	_____  Not applicable	___/___/___  Not applicable
	___/___/___  prn	___/___/___  Still prescribed at [INDEX DATE]	_____	 Increase  Decrease  Remained the same  Not applicable	_____  Not applicable	___/___/___  Not applicable
	___/___/___  prn	___/___/___  Still prescribed at [INDEX DATE]	_____	 Increase  Decrease  Remained the same  Not applicable	_____  Not applicable	___/___/___  Not applicable

Seroquel XR Treatment

Was the patient experiencing psychotic symptoms at initiation of Seroquel XR?

- Yes
- No
- Unknown

Which disorder was Seroquel XR prescribed for?

Please select all that apply

- MDD
- Schizophrenia
- Bipolar disorder
- Other – please specify _____

How many times has the investigator seen this patient since initiation of Seroquel XR?

__ visits

What is your estimate of patient adherence to the prescribed treatment regimen that included Seroquel XR for depression?

___ % of time adherent to prescribed dose(s) (range: 0 – 100%)

(Investigator assessment)

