In the table below record the number of different **dosages of Seroquel XR** prescribed for this patient. Please indicate by ticking in the appropriate boxes the **different dosages** that this patient has experienced, then please enter the **number of prescriptions** for each selected dosage and the **duration (or days supply) of each prescription**.

Dosage of Seroquel XR prescribed	Number of prescription for each dosage	Duration of each prescription (in days)
 50 mg / day	__ scripts	Script 1: __ days, Script 2: __ days, Script 3: __ days, Script 4: __ days Script 5: __ days, Script 6: __ days, Script 7: __ days, Script 8: __ days
 100 mg / day	__ scripts	Script 1: __ days, Script 2: __ days, Script 3: __ days, Script 4: __ days Script 5: __ days, Script 6: __ days, Script 7: __ days, Script 8: __ days
 150 mg / day	__ scripts	Script 1: __ days, Script 2: __ days, Script 3: __ days, Script 4: __ days Script 5: __ days, Script 6: __ days, Script 7: __ days, Script 8: __ days
 200 mg / day	__ scripts	Script 1: __ days, Script 2: __ days, Script 3: __ days, Script 4: __ days Script 5: __ days, Script 6: __ days, Script 7: __ days, Script 8: __ days
 250 mg / day	__ scripts	Script 1: __ days, Script 2: __ days, Script 3: __ days, Script 4: __ days Script 5: __ days, Script 6: __ days, Script 7: __ days, Script 8: __ days
 300 mg / day	__ scripts	Script 1: __ days, Script 2: __ days, Script 3: __ days, Script 4: __ days Script 5: __ days, Script 6: __ days, Script 7: __ days, Script 8: __ days
Other 1: _____ mg / day	__ scripts	Script 1: __ days, Script 2: __ days, Script 3: __ days, Script 4: __ days Script 5: __ days, Script 6: __ days, Script 7: __ days, Script 8: __ days
Other 2: _____ mg / day	__ scripts	Script 1: __ days, Script 2: __ days, Script 3: __ days, Script 4: __ days Script 5: __ days, Script 6: __ days, Script 7: __ days, Script 8: __ days
Other 3: _____ mg / day	__ scripts	Script 1: __ days, Script 2: __ days, Script 3: __ days, Script 4: __ days Script 5: __ days, Script 6: __ days, Script 7: __ days, Script 8: __ days

Prior to initiating SEROQUEL XR, what was the patient response to their most recent prior antidepressant treatment?

		Side effects			

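### Two Appendix B items, the Seroquel XR dosage table and the visit count, do not apply the index-date cut-off of section 2.1 and record undated totals that cannot be cut back at analysis

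*Protocol*

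**What the plan says.** Section 2.1 sets the rule: "Data on drug utilisation will be censored on the index date". The stated purpose is to keep the study from affecting prescribing. Accordingly, "All study sites within a country will be assigned the same index date and will not be contacted prior to the index date". Section 4.2.1 repeats that "Contact with investigators and site preparatory activities are initiated following the index date", and places abstraction later still: "Once site preparatory activities are concluded, including the obtaining of informed consent from the patient, data abstraction of patient medical records" begins.

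Appendix B collects Seroquel XR use in two places.

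- **MDD Treatment.** Both drug tables are limited to the 12 months ending at the index date. In the table of concurrent treatments, each Seroquel XR dose change is a separate line with start date, end date and dose. A box marks drugs still prescribed on the index date.
- **Seroquel XR Treatment.** This section has its own heading and states no such limit. The dosage table asks for the dosages "prescribed for this patient. Please indicate by ticking in the appropriate boxes the" dosages experienced, with the number of prescriptions at each dose and the days covered by each. The visit item asks "How many times has the investigator seen this patient since initiation of Seroquel XR".

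Section 9.2 plans to summarise the "number of visits to the psychiatrist during the timeframe that Seroquel XR has been prescribed", and section 4.2.2 lists the same variable under drug utilisation. Section 4.2.2 also lists prescription frequency and days' supply by dose. Section 9.3 summarises maximum dose, modal dose and duration at each dose, and does not say which table supplies them.

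**The concern.** By the time the form is completed, the record can hold prescriptions and visits later than the index date. Only the wording of the form and the instructions to the abstractor keep them out. The MDD Treatment section repeats the cut-off. The two items in the next section omit it, so an abstractor who follows them literally will record everything up to the day of abstraction.

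Two things are at stake. First, the totals would depend on how late a site was abstracted. Section 1.1 makes differences between countries an objective, and index dates and site preparation are arranged country by country, so unequal lags could look like unequal practice. Second, the visit item does not measure the planned variable. For a patient who stopped Seroquel XR, it also counts visits made after stopping, even those before the index date.

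**Working it through.** The protocol gives no figure on this point to reproduce. The check is a comparison of wording, followed by a calculation of scale on stated assumptions.

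**1. End date and dating of each item**

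| Item in Appendix B | End date on the form | Entries dated? | Can it be cut at the index date later? |
|---|---|---|---|
| Concurrent drug table | Index date | Yes, start and end per dose | Already bounded |
| Dosage table | None | No, counts and days only | No |
| Visit item | None | No, one number | No |

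The opening instruction of the patient form mentions two dates, the second being the index date. It uses them to say which patients the questions concern, not which prescriptions or visits to count. The date of last consultation, asked at the end of the form, has no index-date limit and cannot date individual visits.

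**2. Which planned variables depend on the unbounded items**

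- Prescription frequency and days' supply by dose (section 4.2.2): the dosage table is the only source.
- Visits (sections 4.2.2 and 9.2): the visit item is the only source.
- Maximum dose, duration at each dose and a modal dose based on time (section 9.3): these can be derived from the dated table. Patients enter by starting treatment "during a 9 month period corresponding to 3 to 12 months following the launch", and the dated table reaches back 12 months from the index date, so it covers the whole pre-index exposure.

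**3. Scale, for illustration**

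Input from section 2.1: a 9-month inception window ending at about the index date.

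Assumptions, none given in the protocol: initiation uniform over the 9 months; abstraction L months after the index date; a constant monthly stopping rate m.

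With u the time from initiation to the index date, uniform on 0 to 9:

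- No stopping: pre = 9/2 = 4.5 months and post = L, so the post-index share is L/(4.5 + L).
- With stopping: pre = mean of (1 − e^(−mu))/m, and post = mean of e^(−mu) × (1 − e^(−mL))/m. The share is post/(pre + post).

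| m per month | Pre (months) | L = 1 | L = 3 | L = 6 |
|---|---|---|---|---|
| 0 | 4.50 | 1/5.5 = 18% | 3/7.5 = 40% | 6/10.5 = 57% |
| 0.10 | 3.41 | 0.63/4.04 = 16% | 1.71/5.12 = 33% | 2.97/6.38 = 47% |

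For m = 0.10, the proportion still on treatment at the index date is (1 − e^(−0.9))/0.9 = 0.66. Hence pre = (1 − 0.66)/0.10 = 3.4, in line with the table.

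These are shares of recorded prescribed time. They do not estimate a shift in any dose summary.

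**The case against.** The best defence is that section 2.1 is a study-wide rule. It covers both items, since section 4.2.2 lists visits under drug utilisation. Patient data are abstracted by the sponsor's representative, section 5.1 promises trained abstractors and standard scripts, and a reminder missing from two items does not repeal the rule. This stands in part: post-index data can enter, but nothing shows that they will. It does not remove the defect. The form is the instrument on which the data are recorded, it states the limit elsewhere, and an error at abstraction leaves no trace that would allow correction.

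Three stronger readings are tempting, and the protocol does not support them.

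- A reader might infer that modal dose, maximum dose and duration are contaminated. The dated table gives a bounded source for all three, and section 9.3 leaves the choice open, which an analysis plan may settle.
- A reader might infer that everything after the index date is influenced by the study. Sites are contacted on or after that date, so prescribing between the index date and first contact cannot be. A visit for consent is counted only if consent is obtained at a visit.
- A reader might treat the added observation time as bias. Lag over 4.5 months gives 3/4.5 = 67% more time at a 3-month lag, but only if nobody stops, and longer observation does not by itself shift a dose distribution.

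**Conclusion.** The point holds for prescription frequency by dose, days' supply by dose and the visit count. Completed as worded, these items do not deliver the censoring of section 2.1, and their undated entries prevent later correction. The mismatch between the visit item and section 9.2 holds whatever is decided about the dose tables. For modal dose, maximum dose and duration the exposure is conditional on using the undated table.

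The size is unknown. Between 16% and 57% of recorded prescribed time could be post-index, for assumed lags of 1 to 6 months and assumed monthly stopping of 0 to 10% with uniform entry. No figure in the protocol is contradicted, and all analyses are descriptive. The importance is therefore moderate, but the correction should be made because section 5 singles out dose distribution and the data cannot be repaired after abstraction.

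**What to change.** 1. **Dosage table:** limit it to prescriptions issued from Seroquel XR initiation up to and including the index date. For a prescription that spans the index date, count days' supply only up to that date.
2. **Visit item:** ask for visits from initiation until Seroquel XR was stopped or the index date, whichever came first. This matches sections 4.2.2 and 9.2 and adds the cut-off of section 2.1.
3. **Section 9.3:** name the dated concurrent-treatment table as the source for maximum dose, modal dose and duration by dose.
4. **eCRF:** raise a query when total truncated days' supply across all doses exceeds the time from initiation to the index date. A check made dose by dose would not serve: it misses an overrun spread over several doses, and, without truncation, it would flag a valid prescription written shortly before the index date.

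The cost is a few lines of form wording and one eCRF query. No extra data source is needed, because the abstractor already works from the full record.

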3.3.1 Inclusion Criteria for Patients

1. Provision of informed consent before initiation of any collection of questionnaire data.
2. Female and male aged 18 years and over.
3. Documented clinical diagnosis of Major Depressive Disorder, Single Episode, or Recurrent.
4. Initiation of Seroquel XR for treatment of MDD during the period defining the inception cohort, i.e. from 3 months after launch until the index date.

The prescription of the medicinal product is clearly separated from the decision to include the patients in the study.

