9. ANALYSIS

Data obtained from the drug utilisation questionnaire will be reported descriptively. No statistical comparison will be conducted. Summary statistics will be provided. There will be no imputation for any missing values. For continuous variables, the number of responses, mean, median, minimum, maximum, and standard deviation will be provided. For discrete variables, the number of responses and proportion represented by each category will be summarized. Prescribing practices and drug utilisation data will be reported by country permitting comparisons across countries.

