 Yes  No  Unknown	 Yes  No  Unknown

MDD Treatment

This section is dedicated to recording **drug treatments** received by this patient for his / her MDD in the **12 months up to [INDEX DATE]**.

In the table below, please list **ALL drug treatments for MDD** that started and ended before the initiation of Seroquel XR received by the patient in the 12 months up to [INDEX DATE]. **Please include any drug treatments for MDD noted in the patient's medical record that were prescribed either by the investigator or by other physicians.** Also, for each drug treatment, please specify information on start and end date and dosing. Please record **all changes in dose** as separate line entries.

(1) Specific drug name (generic or brand names)	(2) Start date (day/mth/year) Check for "on demand" or prn use	(3) End Date (day/mth/year)	(4) Dose (specify Unit)
	-- / / --  prn	-- / / --	_____
	-- / / --  prn	-- / / --	_____
	-- / / --  prn	-- / / --	_____
	-- / / --  prn	-- / / --	_____
	-- / / --  prn	-- / / --	_____
	-- / / --  prn	-- / / --	_____

In the table below, please list **ALL drug treatments for MDD** that were **prescribed concurrently with Seroquel XR** (including Seroquel XR) received by the patient in the 12 months up to *[INDEX DATE]*. **Please include any drug treatments for MDD noted in the patient’s medical record that were prescribed either by the investigator or by other physicians.** Also, for each drug treatment, please specify information on start and end date (if applicable), dosing and dates of dose changes.

For Seroquel XR prescriptions, please record all changes in dose as separate line entries using columns (1) – (4).

Instructions: Please answer these questions for ALL drug treatments for MDD that were prescribed by the investigator or other physicians concurrently with Seroquel XR For Seroquel XR, please record all changes in dose as separate line entries
				
Instructions: Please answer these questions only for drug treatments for MDD that were prescribed by the investigator or other physicians concurrently with Seroquel XR
		

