		None	Did not significantly interfere with Subject's functioning	Significantly interfered with Subject's functioning	Outweighed therapeutic effect (Not tolerable, Needed to stop medication)
Therapeutic effect	Marked vast improvement. Complete or nearly complete remission of all symptoms				
	Moderate improvement. Partial remission of symptoms				
	Minimal slight improvement				
	Unchanged or worse				

Unknown or Not assessed
(Investigator assessment)

When was the last consultation date for this patient?

__ / __ / ____
day / mo / year

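### The prior-antidepressant response item in Appendix B has no answer for patients who had no earlier antidepressant, so within that item they are mixed with missing data

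*Protocol*

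**What the plan says.** The item sits in the Seroquel XR Treatment part of the patient form (protocol, Appendix B) and is marked as an investigator assessment. It asks: "Prior to initiating SEROQUEL XR, what was the patient response to their most recent prior antidepressant treatment". The answer is one cell of a 4 by 4 grid, therapeutic effect against side effects. The lowest effect row reads "Unchanged or worse". The only answer outside the grid is "Unknown or Not assessed".

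Section 2.1 defines the inception cohort as "patients initiating Seroquel XR (as add-on therapy or as monotherapy) during a 9 month period". Section 3.3.1 asks for consent, adult age, a documented diagnosis of MDD (single episode or recurrent), and initiation of Seroquel XR for MDD "from 3 months after launch until the index date". Neither section requires an earlier antidepressant.

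Appendix B has two drug tables. The first takes drugs for MDD "that started and ended before the initiation of Seroquel XR received by the patient in the 12 months up to [INDEX DATE"]. The second takes drugs for MDD prescribed alongside Seroquel XR over the same 12 months, with start dates. Both include prescriptions by other physicians. Elsewhere the form asks for the month and year of the first depressive episode and of the MDD diagnosis, each with an unknown box.

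On reporting, Section 9 says: "Data obtained from the drug utilisation questionnaire will be reported descriptively". Discrete items are given as counts and proportions per category, nothing is imputed, and utilisation data are shown by country.

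**The concern.** A closed question should have a valid answer for every eligible patient. This one does not. If the patient had no earlier antidepressant, every grid cell is false and the only remaining tick means that the response is not known or was not assessed. A known fact about treatment history is then recorded as an absence of information.

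The second objective in Section 1.1 is to describe differences between countries in treatment practice involving Seroquel XR. Section 2.1 describes the approval as being for add-on treatment, so whether an antidepressant came first, and how the patient responded, is part of the picture that such a study would be expected to give. If first-line use differs between countries, this item would show part of that difference as a difference in missingness. Once two groups have been recorded under one tick, no analysis of that item can separate them.

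**Working it through.** There is no stated figure to reproduce. The check sets the response options against eligibility and then asks what the rest of the form can recover.

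**1. Response options.** The grid has 4 × 4 = 16 cells, and the combined answer makes 17. All 16 cells describe the effect and tolerability of a treatment that was given. That includes the lowest effect row, which reports no benefit from a drug taken rather than no drug. The seventeenth answer concerns a response that is unknown or was not assessed. No option means none given. By contrast, columns 5 to 7 of the concurrent-drug table in the same form each have a not-applicable box.

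**2. Eligibility.** Monotherapy initiators and single-episode patients are admitted, and no criterion asks for previous treatment. Patients with no earlier antidepressant can therefore enter. Starting as monotherapy does not by itself mean that none was given before, so monotherapy cannot stand in for first-line use.

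**3. Look-back of the drug tables.** Inputs: the tables cover the 12 months up to the index date (Appendix B), the index date is about 12 months after launch, and initiation falls between months 3 and 12 (both Section 2.1).

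- Look-back before initiation = 12 − (months from initiation to index date).
- Initiation at month 3: 12 − (12 − 3) = 3 months.
- Initiation at the index date: 12 − 0 = 12 months.

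For the earliest starters, an antidepressant that ended more than about 3 months before Seroquel XR lies outside the window.

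**4. What the rest of the form can settle.**

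| Recorded elsewhere in the form | What it shows |
|---|---|
| Concurrent antidepressant with a start date before Seroquel XR | Not first line |
| Antidepressant listed in the table of drugs ended before Seroquel XR | Not first line |
| No earlier-started antidepressant listed; first episode dated inside the window | Probably first line |
| No earlier-started antidepressant listed; first episode before the window or undated | Cannot be decided |

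In the last row, an empty entry may mean never treated, treated and stopped before the window, or treated but not recorded. With no box for none on the table, these three look alike. The third row stays at probable for the same reason: an empty table does not distinguish no drug from no record.

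**The case against.** The best case against the point is that the dataset holds more than this one item. The drug tables ask for all MDD drugs, carry start dates and include other prescribers. Section 4.2.2 allows patient-reported history where the physician has treated the patient for less than 12 months. Episode dates help with recent-onset illness. Whether Seroquel XR was used as add-on can be read from the concomitant antidepressants at initiation, which Section 9.3 already summarises by country. This largely stands. It rules out the stronger reading that a reader might infer, namely that first-line use is lost from the study data or that the tables recover nobody. What survives is the last row of the table above.

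A second objection is that Sections 9.2 to 9.4 do not name prior response as an output, and that its tabulation may be left to an analysis plan. That is also fair. The item is covered only by the general statement in Section 9. Section 9.3 does list a Clinical Global Impression at initiation, and no other item in the questionnaire as shown looks able to supply it, but that link is an inference. Still, the defect lies in data capture, and a later plan can cross-classify only what was recorded.

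Third, Sections 4.1.2 and 4.2.2 allow revision after the pilot, so the gap may be noticed. It may also pass. Section 4.1.1 accepts face validity when no more than 5% of items are flagged by both psychiatrists, and one flagged item stays within that limit on any form of 20 or more items (1/20 = 5%). The revision route is a reason to make the change there, not a reason to leave it.

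**Conclusion.** The point holds for this item. An eligible patient with no earlier antidepressant has no valid answer and is recorded together with missing data. The rest of the form narrows the ambiguity but leaves a residual group, and the look-back is shortest for those who started soonest after month 3.

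The documents give no rate of first-line use, of unknown response, or of how either varies by country. A reader might want to attach a percentage-point distortion to the country comparison, but any such figure would only return the rates assumed for it, so none is given. That the effect differs between countries is a possibility, not something the documents show.

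The weight is modest. Eligibility, sampling and the dose proportions behind Table 2 are untouched. The conclusion assumes that some eligible patients had no earlier antidepressant, which the criteria allow but do not quantify, and that the form shown is the one to be used.

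**What to change.** In the Appendix B response item, add a separate box, *No antidepressant treatment before Seroquel XR*, distinct from the existing unknown or unassessed answer. Do this when the questionnaire is revised after the pilot and before it is translated, which under Section 4.1.3 follows validation.

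Where the item is tabulated by country, show that category on its own line and give response percentages among patients with an earlier antidepressant and a known response, with the unknown count beside them.

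The cost is one tick box in the form and eCRF and one extra table row. The item is already an investigator assessment, so no added visit or record search is needed. After abstraction is complete, the residual group could be resolved only by going back to the sites.
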